10.13.9 Time to Response (TtR and iTtR)

- Per RECIST (v1.1): TtR is defined as the time from the first day of study treatment until the first date of confirmed PR or CR. The date of confirmed response would be the date of the first PR or CR that is confirmed by a later PR or CR.
- Per iRECIST: iTtR is defined as the time from the first day of study treatment until the first date of iPR or iCR. The date of confirmed response would be the date of the first iPR or iCR that is confirmed by a later iPR or iCR.

Time to response is only calculated for patients with measurable disease.

10.13.10 CTC Response

The CTC response is defined as the proportion of patients with CTC count conversion from ≥ 5 at baseline to < 5 cells at any post-baseline timepoint per 7.5 mL of blood. This endpoint applies to the mCRPC cohort only.

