### 1.3.3 Collection of blood samples, nanrilkefusp alfa combined with pembrolizumab

All attempts should be made to collect the samples on time.

Cycle	Screening	Cycle 1						Cycle 2					Cycle 3				From cycle 4				End of treatment
		1	2	6	8	9	13	1	2	6	8	9	1	2	8	9	1	2	8	9	
Nanrilkefusp alfa administration 		X	X		X	X		X	X		X	X	X	X	X	X	X	X	X	X	
Pembrolizumab administration 		X						X					X				X				
Serum for nanrilkefusp alfa PK													See section 1.3.5								
Serum for cytokines 		X	X		X	X		X	X		X	X									
Serum for nanrilkefusp alfa immunogenicity 		X						X									Cycle 4 only				X
Serum for pembrolizumab PK 		X						X									Cycles 4 and 8 only				X
Serum for pembrolizumab immunogenicity 		X						X									Cycle 4 only				X
Whole blood for RNA and DNA analysis 		X		X				X		X											
HIV, HBV, and HCV	X																				
Hematology (full complete blood count including absolute lymphocyte count)	X	X 	X 	X	X 	X 	X	X 		X	X 		X 		X 		X 		X 		X
Biochemistry (including C-reactive protein)	X	X 	X 	X		X 	X	X 		X		X 	X 		X 		X 		X 		X
Creatinine clearance	X	X 		X		X 		X 		X		X 	X 		X 		X 		X 		
C-reactive protein				X 					X 		X 										
Coagulation	X	X 		X 				X 		X 			X 		X 		X 		X 		X
TSH, T3 or free T3, free T4	X	X 											X 				X 				X
Patients with mCRPC: PSA, alkaline phosphatase, lactate dehydrogenase, CTCs, circulating tumor DNA fraction	X		X 										X 				X 				
Serum pregnancy	X																				

1. Time to be recorded
2. Time to be recorded; pembrolizumab will be administered within 30 minutes following nanrilkefusp alfa administration.
3. Before nanrilkefusp alfa administration and 4 hours ( $\pm 30$  min) after nanrilkefusp alfa administration
4. Within 1 day before nanrilkefusp alfa administration

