#### Disease characteristics

4. Patients with the following histologically or cytologically confirmed solid tumor indications and line of treatment:
  - NSCLC
    - For the second-line or third-line treatment of patients with advanced and/or metastatic NSCLC with disease progression on or after an immune checkpoint inhibitor-containing regimen and a platinum-containing regimen, with no EGFR or ALK genomic tumor aberrations, and who are not amenable to curative treatment
  - Colorectal cancer
    - For the first-line treatment of patients with unresectable or metastatic MSI-H/dMMR colorectal cancer
  - cSCC
    - For the first-line treatment of patients with recurrent or metastatic cSCC or second line if refractory or relapsed after an immune checkpoint inhibitor-containing regimen, and in whom radiotherapy is not feasible (based on data from study SC103 [AURELIO-03])
  - Advanced hepatocellular carcinoma (not applicable in France)
    - For the second- to fourth-line treatment of patients with advanced hepatocellular carcinoma having progressed on or after a checkpoint inhibitor-containing regimen
  - mCRPC
    - For the second- to fifth-line treatment of patients with mCRPC after recurrence or failure of docetaxel and prior treatment with abiraterone, enzalutamide, or any other androgen receptor-targeted agent
  - Ovarian cancer
    - For the second- to fifth-line treatment of patients with advanced ovarian cancer after recurrence or failure on the last platinum-based therapy within 6 months
5. Have measurable disease per RECIST 1.1 as assessed by the local site investigator/radiology; lesions situated in a previously irradiated area are considered measurable if progression has been demonstrated in such lesions

mCRPC: Patients with both measurable and non-measurable disease will be enrolled. At least 35 patients with measurable disease will be enrolled. Patients with no measurable disease and only widespread bone disease must have a CTC count of  $\geq 5$  cells per 7.5 mL of blood.

6. Availability of tumor tissue from a fresh biopsy at screening unless the biopsy cannot be obtained due to safety reasons or non-accessibility of the tumor site. If it is not possible to obtain a fresh biopsy, every effort should be taken to retrieve an archival biopsy. Archived, fixed tumor tissue may only be collected if taken preferentially after completion of the most recent systemic tumor therapy and within 12 months prior to the first dose of study treatment.

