### 9.3 Statistical analyses

#### 9.3.1 General considerations

Analyses will be descriptive (i.e., without a comparison). Efficacy analyses will be performed for each indication separately. Safety will be analyzed as described in section [9.3.3](#).

Summary statistics will include:

- Counts and percentages (categorical data)
- Number of observations, mean, standard deviation, median, minimum, and maximum (continuous data)

The ORR, iORR, BOR, iBOR, CBR, iCBR, CTC response, and PSA response will use the exact method based on the binomial distribution[56](#) to derive 95% confidence intervals (CIs).

---

Kaplan-Meier estimations and estimations of median (if reached) with log-log 95% CI, Q1 (25th percentile), and Q3 (75th percentile) will be used for time to confirmed PSA progression (mCRPC only), DoR, iDoR, PFS, iPFS, TtR, iTtR, and OS. In case of a confirmed response or disease progression, the date of the first tumor assessment or PSA evaluated as response or progression will be used for the time-to-event variables.

Depending on the amount of missing data, a sensitivity analysis will be performed for time-to-event endpoints. If such an analysis is planned, it will be described in the final Statistical Analysis Plan (SAP).

The last value of PSA, CTC count, CT scan, bone scan, or MRI on or up to 28 days before the date of the first study treatment will be used as the baseline value for each assessment. Only tumor assessments prior to or at the date of initiation of further-line therapy and using CT scan, bone scan, or MRI will be used for the evaluation of tumor response.

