PFS and iPFS are defined as the time from the first day of study treatment until the first date of radiological disease progression or death and will be summarized using Kaplan-Meier estimates for each indication separately.

Patients with missing data will be censored/considered as having an event as specified below:

Situation	Date of progression or censoring	Outcome
Incomplete or no baseline tumor assessment	Date of the first day of study treatment	Censored
Start of new anti-cancer therapy	Date of the last tumor assessment with non-progression before the start of new anti-cancer therapy	Censored
Death before the first disease progression assessment	Date of death	Progressed
Death between adequate tumor assessment visits	Date of death	Progressed
Progression or death after one missed adequate tumor assessment	Date of progression or death, whichever is earliest (if both occur)	Progressed
Progression or death after more than one missed adequate tumor assessment	Date of the last evaluable tumor assessment	Censored
No progression, no death	Date of the last evaluable tumor assessment	Censored

- TtR and iTtR

TtR and iTtR are defined as the time from the first day of study treatment until the first date of partial response (PR, iPR) or complete response (CR, iCR) and will be summarized using Kaplan-Meier estimates for each indication separately. Patients with missing data will be censored at the last assessment date, date of death, or date of the first day of study treatment (if incomplete or no baseline tumor assessments), whichever occurs latest.

- CTC count conversion from  $\geq 5$  to  $< 5$  cells per 7.5 mL of blood

The CTC response is defined as the proportion of patients with CTC count conversion from  $\geq 5$  to  $< 5$  cells per 7.5 mL of blood and will be analyzed and presented as a point estimate and a 95% CI for the mCRPC indication. Patients with missing data will be considered as non-responders.

- Confirmed PSA decline of  $\geq 50\%$

The PSA response is defined as the proportion of patients with a PSA decline of  $\geq 50\%$  and will be analyzed and presented as a point estimate and a 95% CI for the mCRPC indication.

Responses will need confirmation by a second consecutive value obtained 4 or more weeks after the first value indicated a response. Response will be evaluated 6 months post trial entry. Evaluable patients with no confirmed response as defined above will be classified as non-responders.

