10.2 Baseline

Unless otherwise specified, baseline is defined as the last non-missing value prior to the first administration of either study treatment.

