12.7.8 CTC Response

The CTC response will be summarized using descriptive statistics (frequency and percentage) together with a 95% CI for the mCRPC indication cohort. Patients with missing data will be considered as non-responders.

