12.7.9 PSA Response

The PSA response will be summarized using descriptive statistics (frequency and percentage) together with a 95% CI for the mCRPC indication cohort.

Responses will need confirmation by a second consecutive value obtained 4 or more weeks after the first value indicated a response. Evaluable patients with no confirmed response as defined above will be classified as non-responders.

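### CTC response in mCRPC rests on one unconfirmed count below 5, so some patients near the cut-off will convert with no drug effect; report a confirmed rate beside it

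*SAP*

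**What the plan says.** - **Response rule.** Protocol 9.3.3.2: "The CTC response is defined as the proportion of patients with CTC count conversion from" at least 5 to below 5 per 7.5 mL, with no timepoint given. SAP 10.13.10 completes this as a fall from at least 5 at baseline to "< 5 cells at any post-baseline timepoint per 7.5 mL of blood".
- **Analysis.** SAP 12.7.8: "The CTC response will be summarized using descriptive statistics (frequency and percentage) together with a 95% CI for the mCRPC indication cohort". Missing data count as non-response. Confirmation, a landmark visit and a minimum fall are not mentioned.
- **Baseline.** One value. SAP 10.2: "baseline is defined as the last non-missing value prior to the first administration of either study treatment". Protocol 9.3.1: "The last value of PSA, CTC count, CT scan, bone scan, or MRI on or up to 28 days before the date" of first treatment.
- **Sampling.** In Protocol 1.3.3 the row "Patients with mCRPC: PSA, alkaline phosphatase, lactate dehydrogenase, CTCs, circulating tumor DNA fraction" shows screening, an early pre-dose sample (its column is unclear in the extracted table), cycle 3, and then every other cycle from cycle 4.
- **Contrast with PSA.** SAP 10.13.11 also accepts any post-baseline timepoint, but SAP 12.7.9 adds: "Responses will need confirmation by a second consecutive value obtained 4 or more weeks after the first value indicated a response".
- **Entry.** Protocol 5.1, criterion 5: "Patients with no measurable disease and only widespread bone disease must have a CTC count of" at least 5 per 7.5 mL. Patients with measurable disease have no CTC minimum.

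**The concern.** The endpoint dichotomises a small count at 5, requires one observed value on the high side, and then takes the most favourable of several later values. A patient with 5 cells at baseline, 4 at one visit and 20 at the next is a responder. Selection on a single baseline count of at least 5 brings regression to the mean. Each further sample adds another chance of a low count, so patients who stay on treatment longer have more chances to be scored as responders.

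The trial has no control arm from which to subtract this background, and the 95% CI covers sampling error only, not this bias. SAP 6.1 drops the exploratory endpoints after the August 2023 futility analysis, but CTC response is secondary and will still be reported. A reader could take a modest CTC response rate as activity when part of it is measurement.

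**Working it through.** The plan states no rate, benchmark or power for CTC response, so there is no figure of its own to reproduce. The question is what the rule yields when treatment does nothing.

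**Step 1: one patient, Poisson noise only.** Assume counts are Poisson with an unchanged true mean λ. Then p = P(X ≤ 4). Over k independent post-baseline samples the any-visit rule gives 1 − (1 − p)^k. Two consecutive counts below 5 within four samples have probability 3p² − 2p³. Example at λ = 7: p = 0.173; any of four = 1 − 0.827⁴ = 0.53; confirmed = 3(0.0299) − 2(0.0052) = 0.08.

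| λ | One sample | Any of 2 | Any of 4 | Two consecutive of 4 |
|---|---|---|---|---|
| 5 | 44% | 69% | 90% | 41% |
| 6 | 29% | 49% | 74% | 20% |
| 7 | 17% | 32% | 53% | 8% |
| 8 | 10% | 19% | 34% | 3% |
| 10 | 3% | 6% | 11% | 0.3% |
| 15 | 0.09% | 0.2% | 0.3% | about 0 |

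**Step 2: a cohort.** Assume log-normal true means between patients (log-SD 1.3), gamma within-patient variation with CV 30%, and Poisson counts on top. Keep only patients whose simulated baseline is at least 5, and apply no treatment effect.

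| Median true count | 1 sample | 2 samples | 4 samples | 4 samples, two consecutive | 4 samples, Poisson only |
|---|---|---|---|---|---|
| 10 | 11% | 17% | 24% | 9% | 19% |
| 20 | 6% | 10% | 14% | 5% | 11% |
| 40 | 3% | 5% | 7% | 2% | 5% |

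**Step 3: sensitivity.** With log-SD 1.0, median 10, CV 30% and four samples, the rate is 27%. With log-SD 1.0, median 40 and Poisson noise only, it is about 1% with one sample and 3% with four. Placing the median at the cut-off itself (5, log-SD 1.0, Poisson only) gives 36% with four samples, and 16% confirmed; that is an extreme assumption.

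**Step 4: denominator.** The rates above condition on baseline at least 5. Neither document says that the reported proportion does. If all mCRPC patients are counted, the 24% becomes about 17%, because only about 0.7 of the simulated patients have a baseline of at least 5 (0.24 × 0.7 = 0.17).

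**Step 5: how long four samples take.** If post-baseline sampling starts at cycle 3, the fourth sample falls on day 1 of cycle 8 or 9, that is 7 × 3 = 21 or 8 × 3 = 24 weeks after first dose. Patients who stop early are closer to the one-sample column.

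**The case against.** The protocol itself labels PSA decline as confirmed and CTC conversion not, so the SAP follows the protocol's definition. Replacing that definition in an open-label trial after the futility readout would be a post hoc change. This stands, and is why the confirmed rate should be added rather than substituted.

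The size rests on assumptions. The documents give no CTC distribution or variability, the upper figures need a low median, extra-Poisson variation and about 21 to 24 weeks on treatment, and under Poisson noise alone the effect vanishes at true means of about 15. This also stands.

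Four stronger readings are tempting, and the documents do not support them:

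- *Noise explains the CTC responses generally.* It does not explain conversion from high counts; the problem belongs to patients near the cut-off.
- *Sharing the cut-off with the entry criterion adds bias.* The endpoint already conditions on baseline at least 5, so the entry rule adds no noise. It only means that bone-only patients enter with no margin. If the early pre-dose sample precedes first dose and becomes the baseline, those patients need two counts of at least 5, and the 24/14/7% falls to about 17/10/5%.
- *CTC is the only response rate in this cohort without confirmation.* For futility, SAP 11.0 also counts unconfirmed PR and CR in ORR.
- *Patients without measurable disease have little else.* They also have confirmed PSA response, PSA progression, and PCWG3-based BOR, CBR and PFS. By plan they number at most 51 − 35 = 16.

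**Conclusion.** The point holds in limited form. A single count below 5 at any visit, after one baseline count of at least 5, is an unconfirmed rule with an upward bias for patients near the threshold, and the bias grows with the number of samples. Its plausible size is about 1-3% where counts are high or only one sample is taken, up to about 24-27% with a median true count of 10, four samples and 30% within-patient CV. All of these depend on assumed distributions. Confirmation brings the four-sample figures of 24/14/7% down to 9/5/2%, but at a true mean of 5 it still leaves 41%.

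Severity is minor. The endpoint is secondary, analysed descriptively without hypothesis tests (SAP 12.0), and plays no part in the futility rule, which counts objective responses only. The documents set no CTC benchmark, so no decision in the plan turns on this rate. The risk is in how it is interpreted.

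**What to change.** In SAP 10.13.10 and 12.7.8:

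- Keep the protocol-defined any-visit rate and label it as unconfirmed.
- Report beside it, with its 95% CI, a confirmed conversion rate: a count below 5 where the first later CTC sample at least 4 weeks after it is also below 5, with no count of 5 or more in between. Do not tie confirmation to the next scheduled sample, because if sampling runs at cycles 3, 4, 6 and 8, the sample after cycle 3 comes only 3 weeks later.
- State the denominator as mCRPC patients with a baseline count of at least 5.
- Base any claim of CTC activity on the confirmed rate, and record the addition in SAP 6.1.

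The cost is SAP wording and one programming rule, using samples already scheduled. The confirmed rate will be lower. Patients without a second qualifying sample cannot be confirmed, which will affect early discontinuers in particular: as extracted, the CTC row shows no End of treatment sample and the pembrolizumab-only schedule (Protocol 1.3.4) has no CTC row. Showing both rates keeps that loss visible. Confirmation reduces false conversions near the threshold but does not remove them.

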10.13.11 PSA Response

The PSA response is defined as the proportion of patients with PSA decline of $\geq 50\%$ from baseline at any post-baseline timepoint. This endpoint applies to the mCRPC cohort only.

10.13.12 Time to Confirmed PSA Progression

Time to confirmed PSA progression is defined as the time from the first day of study treatment to the date of PSA progression, where PSA progression is defined as the date when an increase of 25% or more and an absolute increase of 2 ng/mL or more from the nadir (or baseline, whichever is lowest) are documented.

For patients who have a decline in PSA during treatment, PSA progression must be confirmed by a second value 3 or more weeks later increased with respect to the nadir PSA (or baseline, whichever is lowest). The date of the first PSA progression will be used; in patients with an unconfirmed PSA progression, date of the first PSA progression will be used if followed by treatment discontinuation.

This endpoint applies to the mCRPC cohort only.

10.13.13 Overall Survival (OS) – Exploratory Analysis, not to be reported

OS is defined as the time from the first day of study treatment until the date of death. Patients with missing data will be censored at the last known date to be alive.

10.13.14 Progression-Free Survival 2 (PFS2)⁽⁵⁾ – Exploratory Analysis, not to be reported

PFS2 time is defined as the time from the first day of study treatment to date of second disease progression while on subsequent systemic anti-cancer therapy, or death from any cause, whichever first.

10.13.15 Last Known Date to Be Alive

The last known date to be alive will be derived for patients at the analysis cutoff using the latest complete date among the following:

- Patient assessment dates (blood draws [laboratory, PK], vital signs, ECOG performance status, ECG, tumor assessments, tumor measurement, or tumor biopsy dates)
- Start and end dates of anti-cancer therapies administered after study treatment discontinuation
- AE start and end dates
- Concomitant medication start and end dates
- Concurrent procedure date
- Date of death collected on the 'Death Details' electronic Case Report Form (eCRF)
- Date of last contact collected on the 'Survival Status' eCRF where status is 'alive'; or date last known to be alive if status is 'unknown'
- Study treatment start and end dates
- Date of discontinuation on disposition eCRF pages (do not use if reason for discontinuation is lost to follow-up).

Only dates associated with actual contact of the patient will be used in the derivation. Dates associated with a technical operation unrelated to patient status such as the date a blood sample was processed will not be used. Assessment dates after the cutoff date will not be applied to derive the last contact date, if applicable.

10.14 Derivations for Exposure Variables

The following variables will be derived for SOT101 and pembrolizumab respectively.

Variable	Definition for SOT101	Definition for pembrolizumab	Definition for combination therapy
Duration of exposure (days)	Last dose date – Start dose date +1	Last dose date – Start dose date +1	Last dose date of either SOT101 or Pembrolizumab, whichever is later – Start dose date of SOT101 or

			pembrolizumab, whichever is earlier +1
Cycle started	A patient is considered to have started a cycle if they received at least one dose of SOT101 in that cycle, per the Study Exposure CRF page.	A patient is considered to have started a cycle if they received at least one dose of pembrolizumab in that cycle, per the Study Exposure CRF page.	A patient is considered to have started a cycle if they received at least one dose of SOT101 and pembrolizumab in that cycle, per the Study Exposure CRF page.
Completed Cycle	A cycle is considered completed if the patient received 4 doses of SOT101 and 1 dose of pembrolizumab in that cycle, or the patient started the next cycle and received at least one dose of SOT101 in that cycle.	A cycle is considered completed if the patient received 4 doses of SOT101 and 1 dose of pembrolizumab in that cycle, or the patient started the next cycle and received pembrolizumab in that cycle.	
Duration of cycle (days)	The day prior to the date of cycle start (day 1 in each cycle) will be considered as the end of the previous cycle. For the last cycle, 21 days will be used.		
Planned cumulative dose (applicable unit)	$(12 \text{ (\mu g/kg/dose)} * 4 \text{ doses}) * \text{Number of cycles started (\mu g/kg)}$	200 mg * Number of cycles started (mg)	
Real dose administered (applicable unit)	$(2 \times \text{Total volume administered}) / \text{patient weight (\mu g/kg)}$	As per CRF (mg)	
Actual cumulative dose (all cycles)	Sum of the real doses ($\mu \text{g/kg}$) administered	Sum of the real doses (mg) administered	
Actual cumulative dose for completed cycles* (Not presented, required for calculation of ADI)	Sum of the real doses ($\mu \text{g/kg}$) administered considering only completed cycles	Sum of the real doses (mg) administered considering only completed cycles	
Duration of exposure (days) for completed cycles *	Considering only completed cycles: End date of last completed cycle – Start dose date of SOT101 or Pembrolizumab, whichever is earlier + 1		
Intended dose Intensity	$12 \text{ (\mu g/kg/dose)} * 4 \text{ doses/ 21 day (\mu g/kg /day)}$	200 mg/ 21 day (mg/day)	
Actual dose intensity (ADI) ($\mu \text{g/kg /day}$) or (mg/day) *	Considering only completed cycles; Actual cumulative dose/ Duration of exposure (days)		
Actual dose intensity by cycle ($\mu \text{g/kg /day}$) or (mg/day) *	Considering only completed cycles: Actual cumulative dose in that cycle / Duration of cycle (days)		
Relative dose intensity by cycle (%)	Considering only completed cycles:		

	100 * (Actual dose Intensity for that cycle/Intended dose intensity for that cycle)	
Overall Relative dose intensity (%) *	Considering only completed cycles: 100 * (Actual dose Intensity /Intended dose)	
Compliance with planned dose (%)	100 * (Actual cumulative dose / Planned cumulative dose at that cycle, taking into account per protocol dose reductions)	

* Only completed cycles as defined should be considered for derivation

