#### 6.5.2.1.3 Restarting study interventions

Patients may not have any dose modifications (no change in dose or schedule) of pembrolizumab in this study, as described in [Table 6.3](#).

If the toxicity does not resolve or the criteria for resuming treatment are not met, the patient must be discontinued from all study interventions.

If the toxicities do resolve and conditions are aligned with what is defined in [Table 6.3](#), the combination of nanrilkefusp alfa and pembrolizumab may be restarted at the discretion of the investigator. In these cases where the toxicity is attributed to the combination or to nanrilkefusp alfa alone, re-initiation of pembrolizumab as a monotherapy may be considered after communication with and agreement by the sponsor.

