#### 6.5.2.3 Other allowed dose interruption for pembrolizumab

Pembrolizumab may be interrupted for situations other than treatment-related AEs such as medical or surgical events and/or unforeseen circumstances not related to study interventions. However, study interventions are to be restarted within 21 days of the originally scheduled dose and within 42 days of the previously administered dose, unless otherwise discussed with the sponsor. The reason for interruption is to be documented in the patient's study record.

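### SAP 10.14 counts as planned only the cycles in which the drug was given, so a skipped pembrolizumab infusion or a wholly withheld SOT101 cycle cannot lower listed compliance

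*SAP*

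**What the plan says.** SAP section 10.14 defines the exposure variables in separate columns for SOT101 (nanrilkefusp alfa in the protocol), pembrolizumab and the combination.

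- **Cycle started.** Pembrolizumab: "A patient is considered to have started a cycle if they received at least one dose of pembrolizumab in that cycle". SOT101: "A patient is considered to have started a cycle if they received at least one dose of SOT101 in that cycle".
- **Planned cumulative dose.** Pembrolizumab: "200 mg * Number of cycles started (mg". SOT101: 12 µg/kg times four doses times the "Number of cycles started".
- **Actual cumulative dose.** Pembrolizumab: "Sum of the real doses (mg) administered", with each dose taken from the CRF. SOT101: the corresponding sum in µg/kg.
- **Compliance.** "100 * (Actual cumulative dose / Planned cumulative dose at that cycle, taking into account per protocol dose reductions".

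Protocol section 6.5.2.1.3 fixes the pembrolizumab dose: "Patients may not have any dose modifications (no change in dose or schedule) of pembrolizumab in this study". Doses can nevertheless be missed. Section 6.5.2.3 states "Pembrolizumab may be interrupted for situations other than treatment-related AEs such as medical or surgical events", and Table 6.2 provides for withholding SOT101. SAP section 12.5.1 puts compliance in a listing only, while dose intensity, cumulative dose and numbers of doses and cycles are summarized.

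**The concern.** A compliance ratio should compare what was given with what was due. Here the denominator depends on the drug having been given: a cycle enters a drug's plan only once a dose of that drug has been received in it. The largest possible omission in a cycle, giving none of the drug, therefore goes unrecorded, while a smaller omission in the same cycle is counted. A reader of the listing could take 100% to mean that every due dose was given when whole cycles of one study drug were missed.

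**Working it through.** The documents state no compliance figure, so there is none to reproduce. I apply the SAP formula to an illustrative patient with six cycles due (my assumption), evaluated at cycle 6.

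**Inputs (SAP 10.14).** SOT101 plan per started cycle: 12 × 4 = 48 µg/kg. Pembrolizumab plan per started cycle: 200 mg.

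**Formulas.** SAP compliance = 100 × actual / (per-cycle dose × cycles in which that drug was given). Comparator = 100 × actual / (per-cycle dose × 6).

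**SOT101**, five cycles fully dosed (5 × 48 = 240 µg/kg), with a varying number of injections in cycle 4:

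| Injections in cycle 4 | Actual (µg/kg) | SAP planned | SAP compliance | Share of dose due (of 288) |
|---|---|---|---|---|
| 4 | 288 | 288 | 100% | 100% |
| 3 | 276 | 288 | 95.8% | 95.8% |
| 2 | 264 | 288 | 91.7% | 91.7% |
| 1 | 252 | 288 | 87.5% | 87.5% |
| 0 | 240 | 240 | 100% | 83.3% |

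The two measures agree until the last row. There the SAP figure rises from 87.5% to 100%, although less drug was given.

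**Pembrolizumab**, six infusions due (1200 mg):

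- One skipped: SAP 1000/1000 = 100%; share of dose due 1000/1200 = 83.3%.
- Two skipped: SAP 800/800 = 100%; share of dose due 800/1200 = 66.7%.
- None skipped, one infusion stopped at 100 mg: 1100/1200 = 91.7% on both.

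**Relative dose intensity (RDI) for comparison.** Intended SOT101 intensity is 48/21 = 2.286 µg/kg/day.

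- Withheld cycle in mid-course: duration 6 × 21 = 126 days, so RDI = (240/126)/(48/21) = 83.3%.
- Withheld cycle last: it does not meet the completed-cycle definition, so duration is 5 × 21 = 105 days and RDI = (240/105)/(48/21) = 100%.

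**Which column applies.** The planned-dose row has entries for each drug, so I use the drug-specific definitions. Under the combination definition (both drugs given), a patient with six pembrolizumab infusions and SOT101 in five cycles would have 1200/(200 × 5) = 120%. That column does not repair the measure.

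**The case against.** Several points on the other side are sound.

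- **Pembrolizumab compliance is not always 100%.** A reader might infer that it is, because the dose is fixed. The numerator is the amount recorded on the CRF, and Table 6.4 of the protocol provides for stopping an infusion; one stopped at half dose gives 91.7%. Skipped infusions are invisible, but partial ones are not.
- **Long gaps are restricted.** Section 6.5.2.3 requires restart within 42 days of the previous dose unless otherwise discussed with the sponsor. One skipped infusion fits (2 × 21 = 42 days); two in succession (63 days) do not without that discussion. The single skip is therefore the fair illustration.
- **A mandated hold is adherence to the protocol.** Whether it should count against compliance is a matter of definition. The SAP is not consistent on it, however: a partly withheld cycle lowers the figure and a wholly withheld one does not, whatever the reason.
- **The formula allows for dose reductions.** This does not help. SAP section 12.8.1 treats temporary discontinuation of SOT101 as a different action from dose reduction, and the withheld cycle has already left the denominator.
- **RDI shows the gap.** It does in mid-course (83.3%), but not when the withheld cycle is the last (100%). A reader might also call 100% compliance beside 83.3% RDI a contradiction. It is not: RDI uses calendar time, and the two measures have different definitions.

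**Conclusion.** The definition is wrong as written, with low impact. Wholly omitted cycles of a drug cannot lower that drug's compliance, and giving no SOT101 in a cycle scores better than giving one injection (100% against 87.5%). One skipped pembrolizumab infusion of six is listed as 100% instead of 83.3% of the dose due.

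This rests on two assumptions: that the drug-specific definition of a started cycle applies, and that the skipped cycle keeps its own number. SAP section 10.7 takes cycle numbers from the database. If a delayed dose is entered as the next cycle, no cycle is missing and only RDI shows the delay. The six-cycle patient is illustrative; the documents do not say how often one drug is omitted for a whole cycle.

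A reader might infer that efficacy results or analysis populations are affected. The documents do not support that. The Efficacy and Per Protocol populations have their own dose counts in SAP sections 9.5 and 9.6, and compliance is confined to a listing.

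**What to change.** In SAP section 10.14, define planned cumulative dose for each drug as the per-cycle dose times the number of cycles due, from first dose up to and including the cycle in which that drug is permanently discontinued, whether or not either drug was given in the cycle. Counting cycles started with either drug would not be enough: for the events in Table 6.3, protocol section 6.5.2.1.1 holds both drugs, and a cycle held for both would still drop out.

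Also state:

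- how cycles due are counted from the database cycle numbers, so that a skipped cycle is distinguished from a delayed one;
- how protocol-mandated holds are treated, with the same rule for partly and wholly withheld cycles.

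Keep the drug-specific count of cycles started as its own row.

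The cost is one SAP definition and a small program change, with no new data. The downside is that listed compliance figures will look less favourable. No clinical rule changes.
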